3.3 Risk/Benefit Assessment

Known Potential Risks (Anticipated Adverse Device Effects)

TELLTALE/BASILICA-specific complications

- Embolization of air, valve debris, atheroma, or thrombus/clot to coronary, cerebral, visceral, or systemic circulation possibly causing symptomatic ischemia/infarction
- Myocardial ischemia or infarction (acute coronary syndrome or heart attack)
- Aortic regurgitation after laceration before TAVR, possibly causing hypotension or cardiogenic shock
- Avulsion or other injury of the native or prosthetic aortic valve leaflet, including leaflet prolapse into the coronary arteries, and including embolism of the leaflet into the coronary, cerebral, visceral, or other systemic arteries
- Inadvertent injury of the mitral valve apparatus requiring transcatheter or surgical repair
- Traversal into the left atrium or other non-target chamber
- Electrical coupling of TELLTALE guidewire and (a) bioprosthetic valve frame, (b) guiding catheters, (c) guidewires and snares causing heating, thromboembolism, tachyarrhythmia, and electrosurgery failure
- Native coronary artery injury from mechanical or electrosurgery injury requiring percutaneous catheter or surgical treatment
- Other arterial perforation or injury or dissection, including requiring surgical treatment
- Failure to engage the intended native or bioprosthetic aortic valve leaflet with TELLTALE system to initiate traversal at the intended location
- Mechanical failure of the TELLTALE Guidewire System including fracture and embolization of the guidewire or of the delivery catheters
- Stroke or transient ischemic attack or paralysis
- Permanent disability
- Death

General complications of TAVR and BASILICA-TAVR catheter procedure including TELLTALE system

- BASILICA failure: Failure to prevent coronary obstruction and acute myocardial ischemia requiring transcatheter therapy including percutaneous coronary stenting in a heterotopic ("snorkel") or orthotopic (through TAVR struts) position, or requiring emergency cardiac surgery repair
- BASILICA failure: coronary obstruction caused by the malorientation of struts of TAVR device, or by fabric skirt of TAVR device, despite successful leaflet laceration
- Hypotension or shock or cardiopulmonary arrest including requiring cardiopulmonary resuscitation, chest compressions, cardioversion/defibrillation, vasoactive medications, and/or mechanical circulatory support and/or extracorporeal membrane oxygenation
- Complications of percutaneous venous and/or arterial access including bleeding, retroperitoneal hematoma, local hematoma, perforation, fistula, pseudoaneurysm, compartment syndrome, peripheral nerve injury, chronic pain, infection, among other things
- Acute kidney injury related to BASILICA requiring temporary or permanent hemodialysis or other medical treatment
- Congestive heart failure, elevated natriuretic peptides, or cardiogenic shock that may require intervention
- Volume overload, pleural effusion, pulmonary edema, dyspnea, edema, pericardial effusion, or other congestion from procedure-related volume perturbations or other heart failure
- Respiratory failure requiring oxygen therapy, mechanical support or mechanical ventilation
- Transcatheter heart valve failure including hypo-attenuated leaflet thickening (HALT), reduced leaflet motion, valvular regurgitation, valvular stenosis, prosthetic valve endocarditis, paravalvular leak, structural deterioration, or non-structural valve dysfunction, and/or murmur
- Infection including device infection, endocarditis, infection of a blood vessel
- Infection or sepsis including access sites, lung, urinary tract, or other system
- Abnormal blood tests including serum chemistry tests (creatinine, troponin), electrolyte imbalance, and including hematology tests (hemoglobin, hematocrit, platelets, white blood cells)
- Hemorrhage requiring transfusion or intervention
- Hemolysis related to blood flow around the lacerated aortic leaflets
- Pain including chest pain, angina, back pain, access site pain, neuropathy, and generalized pain
- Pericardial effusion or tamponade requiring percutaneous or surgical treatment
- Pneumothorax, hydrothorax, and hemothorax
- Cardiac arrhythmia including atrial fibrillation, atrial flutter, ventricular tachycardia, ventricular fibrillation including cardiac arrest requiring cardioversion/defibrillation or cardiopulmonary resuscitation

- Conduction system defect which may require a temporary or permanent pacemaker, for example high-degree atrioventricular block or His-Purkinje block
- Syncope, pre-syncope, seizure, delirium, or other loss of consciousness
- Other venous thrombosis or thromboembolism including deep vein thrombosis, and pulmonary thromboembolism
- Radiation injury including intractable skin injury
- High blood pressure

Allergic or inflammatory reaction to

- anesthesia,
- contrast media,
- materials in the TELLTALE Guidewire System

The Sponsor and investigators recognize these risks are high and reflect the underlying comorbidities, yet consider procedural risks overall to be an acceptable compromise to enable TAVR in patients otherwise ineligible.

Risks related to Radiation

In this research protocol, subjects will be exposed to incremental radiation fluoroscopy to add the BASILICA procedure using the TELLTALE system to conventional TAVR. It is estimated (conservatively) that the amount of research radiation that a subject will be exposed to during participation in this research protocol will be approximately 30mSv from approximately 30 minutes of fluoroscopy during performance of BASILICA-TAVR using TELLTALE. This is equivalent to 750 chest X-rays.

We believe the total fluoroscopy exposure to be justifiable in this setting, given the seriousness of their cardiovascular disease and limited options. We estimate the benefit to the research subjects for these procedures to outweigh the risks.

Risks to privacy: Personal Identifiable Information

Clinical data from subjects participating in this trial will retain personally identifiable information. This includes CT scans, echocardiograms, and medical records.

Abstracted data will be coded (personally identifiable information removed but linking codes retained) and for transmission to participating subcontracting investigators, clinical events adjudication committee, statistician, and to Transmural Systems which is the collaborating manufacturer of the TELLTALE system.

DICOM data will be stored in a secured NIH research PACS system for analysis, including personally identifiable information.

Known Potential Benefits

Subjects are expected to benefit from investigational BASILICA using the TELLTALE purpose-built leaflet traversal and laceration system. TELLTALE BASILICA-TAVR is expected to be non-inferior to bedside-modified and off-label use of devices for electrosurgical traversal and

laceration for BASILICA to prevent acute and subacute coronary obstruction from TAVR. BASILICA is believed to enable TAVR not otherwise possible without “snorkel stenting,” which many physicians believe to be unsafe.

Subjects may also benefit indirectly from increased medical attention from participating in an early feasibility study.

Future patients, and therefore society, may benefit should the TELLTALE system prove safe and effective.

Alternatives to research participation

Candidates for TAVR with BASILICA have no good treatment alternatives. They are not eligible for surgical aortic valve replacement because of high or prohibitive risk of perioperative death or serious morbidity. They are not candidates for conventional TAVR, which risks life-threatening coronary obstruction. TAVR using pre-positioned coronary stents (“snorkel-stents”) risks early and late catastrophic stent failure and coronary obstruction, which has high mortality[[28](#), [29](#)].

Candidates for TAVR with BASILICA who do not consent to participate in this study are eligible for “standard” BASILICA using off-label medical devices, including bedside modification of commercial devices. This approach, developed by the investigators of this trial, has become the “best practice.” Such off-label BASILICA is likely inferior to the research intervention using the TELLTALE guidewire system because of risk of thromboembolism from inferior electrical performance of bedside-modified devices, risks of device fracture or other failure from inferior mechanical performance of bedside-modified devices, risks of mal-preparation during bedside modification including asymmetric denudation, risks of mal-positioning of the lacerating surface in bedside-modified devices, among others. The study devices, which are purpose-built to address these risks, are considered intrinsically superior to bedside-modified devices used off-label.

Assessment of Potential Risks and Benefits

These subjects have few or no good therapeutic alternatives to BASILICA-TAVR and have the potential to benefit from this procedure.

Risk of investigational BASILICA-TAVR using the TELLTALE system is mitigated by including highly capable and experienced operators and highly experienced medical centers. The TELLTALE system device will be used only by interventional cardiologists who have specific expertise in BASILICA and TAVR.

Overall, the potential benefits of participation appear to exceed the risks to the subjects.

4 OBJECTIVES AND ENDPOINTS

4.1 Objective

The objective of this protocol is to test the safety and effectiveness of the TELLTALE guidewire system in accomplishing BASILICA leaflet traversal and laceration to prevent coronary artery obstruction in patients whose native or bioprosthetic TAVR threatens coronary artery obstruction because of narrow sinus of Valsalva and/or sinotubular junction.

An additional objective is added in Amendment B, to offer study expansion to the investigational BASILICA-TAVR using the TELLTALE system for patients with native aortic valve failure at risk of coronary obstruction and who otherwise meet the selection criteria.

4.2 Hypotheses

We hypothesize that the TELLTALE guidewire system traverses and lacerates intended native and bioprosthetic aortic valve leaflets that threaten coronary artery obstruction during TAVR.

We further hypothesize that BASILICA using the TELLTALE guidewire system prevents TAVR-related acute coronary obstruction in patients at risk, and with acceptable safety.

4.3 Endpoint Design Considerations

The intent of this protocol is to demonstrate safety and efficacy of BASILICA-TAVR using the TELLTALE guidewire system to mitigate the risk of TAVR-induced coronary obstruction in at-risk patients. The primary endpoint is selected based on the clinical characteristics and implications of BASILICA success and failure, which are described below.

Definitions of BASILICA Success

BASILICA technical success” in lacerating a leaflet requires successful traversal and successful leaflet laceration only.

“BASILICA procedure success” in preventing coronary obstruction requires successful leaflet traversal and laceration and further requires post-TAVR leaflet splay to preserve coronary artery blood flow. Some causes of BASILICA procedure failure despite BASILICA technical success include

- (1) THV malrotation causing coronary obstruction by the THV struts;
- (2) BASILICA slice malorientation with regard to the ostium of the threatened coronary ostium combined with very small valve-to-coronary distance (VTC); and
- (3) protrusion of aortic leaflet material into the coronary artery after BASILICA and TAVR, either because of bulky leaflet calcification or because of mechanical avulsion rather than electrosurgical BASILICA laceration.

“Facilitated BASILICA procedure success” includes immediate orthotopic coronary stenting to mitigate aortic leaflet protrusion and protect flow to the threatened coronary artery without “snorkel” stenting between the THV and the sinotubular junction. Orthotopic stenting is not possible without BASILICA leaflet laceration. Facilitated BASILICA procedure success is considered clinically acceptable. Sometimes orthotopic-stent-facilitated BASILICA can mitigate THV- or slice- malorientation and preserve coronary flow. While clinically a success, “facilitated BASILICA procedure success” is nevertheless classified as failure in this protocol.

Immediate consequences of BASILICA Failure

Unsuccessful traversal precludes BASILICA. Typically there are no sequelae to failed traversal *per se*. The subject continues to risk coronary obstruction as a consequence of TAVR.

Given successful traversal, the outcomes after attempted laceration are:

- (1) Successful electrosurgical laceration of the native or bioprosthetic leaflet that threatens coronary obstruction after TAVR. Typically there is no immediate hemodynamic compromise after electrosurgical leaflet laceration because appropriately split leaflets continue to coapt and the result is a mild increment in acute aortic regurgitation. After this BASILICA technical success, the results of TAVR will determine BASILICA procedure success as described previously; OR
- (2) Unsuccessful electrosurgical laceration but successful mechanical laceration or avulsion. This is clinically manifest by a significant increment in aortic regurgitation and hemodynamic compromise requiring expedited TAVR. Acute coronary occlusion is typically averted, but orthotopic coronary artery stenting is sometimes required because the avulsed leaflet may prolapse into the target coronary artery ostium. With appropriate operator training, there are typically few sequelae other than orthotopic stenting of a non-atherosclerotic ostial coronary artery. We believe orthotopic stenting is safer than heterotopic (“snorkel”) stenting in which a stent extends far proximal to the coronary ostium and risks mechanical crush by the transcatheter heart valve against the sinotubular junction. Despite these undesirable characteristics, mechanical avulsion can be classified as BASILICA technical success according to our definition; OR
- (3) Aborted or abandoned laceration. Typically there are no sequelae.

BASILICA is considered failed after unsuccessful traversal or after aborted/abandoned laceration. BASILICA may be successful (clinically) after orthotopic stenting, but in this protocol such procedures are classified as unsuccessful investigational BASILICA.

Alternatives to BASILICA, and remaining options after failed BASILICA

Remaining options for the patient after failed BASILICA includes:

- (1) Aborting the TAVR procedure with further consideration for surgical aortic valve replacement despite predicted high or prohibitive risk of death or severe morbidity; OR
- (2) Proceed with TAVR using snorkel stenting (that the study investigators consider inadequate); OR
- (3) Conservative management or hospice; OR
- (4) A repeat attempt at BASILICA during the same, or during a different catheterization procedure.

Implications for trial design

Patients requiring TAVR who are at risk of TAVR-induced coronary obstruction and who are at high or prohibitive risk of surgical aortic valve obstruction have few satisfactory clinical options. Increasing these options beyond zero is desirable.

As described above, BASILICA technical failure typically has no sequelae, and returns patients to their baseline state of high spontaneous risk of adverse outcomes.

Based on our investigational and registry experience with BASILICA using bedside-modified commercial devices off-label, there is no evidence of post-discharge complications of BASILICA[[3](#), [4](#), [24](#)].

Subjects in this trial have an approximately 90% likelihood of acute coronary obstruction after TAVR without BASILICA, and if obstructed, an approximately 40% 30-day mortality. The primary endpoint for this trial captures both technical and clinical safety events, and therefore is appropriate to characterize the safety and efficacy of BASILICA-TAVR using the TELLTALE guidewire system.

4.4 Primary Efficacy Endpoint

The primary efficacy endpoint is **Device (technical) success**, assessed upon exit from the cardiac catheterization laboratory, including all of the following:

- Successful electrosurgical leaflet traversal using the TELLTALE Guidewire, when attempted; and
- Successful electrosurgical leaflet laceration using the TELLTALE Guidewire; and
- Successful retrieval of the TELLTALE Guidewire System

Successful traversal is defined as guidewire traversal from the aortic root across the intended aortic leaflet into the left ventricular outflow tract confirmed by either by angiography or by leaflet traction upon guidewire ensnarement.

Successful laceration is defined as intact liberation of the TELLTALE guidewire loop across a leaflet, with restoration of guidewire mobility allowing removal from the body. It may be confirmed by transesophageal echocardiography.

Successful retrieval of the TELLTALE guidewire is defined as successful removal from the body of an intact TELLTALE guidewire after successful laceration.

Rationale for primary efficacy endpoint

The primary efficacy endpoint tests the efficacy of the TELLTALE guidewire, which according to the Instructions for Use (IFU) is "...indicated for transcatheter electrosurgical traversal and laceration of native and bioprosthetic tissue."

This endpoint tests only the efficacy of the TELLTALE guidewire, not of the BASILICA procedure nor of the TAVR procedure. Safety endpoints are tested in a separate primary safety endpoint.

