The prospective FDA IDE NHLBI BASILICA study enrolled 30 patients at high risk of coronary artery obstruction from TAVR who underwent BASILICA with an Astate guidewire with benchtop modification[3]. All patients were at high risk of coronary obstruction as determined by the NHLBI CT core laboratory. Seven (23%) were double-leaflet BASILICA. Primary success of successful BASILICA and TAVR without coronary obstruction or reintervention was met in 28 (93%) subjects. BASILICA traversal and laceration was successful in 28 (93%) subjects. There was 100% freedom from coronary obstruction and reintervention. Primary safety of freedom from MACE was met in 21 (70%), driven by six (20%) major vascular complications related to TAVR but not BASILICA. There was one death at 30 days. There was one (3%) disabling stroke and two (7%) non-disabling strokes. Transient hemodynamic compromise was rare (7%) and resolved promptly with TAVR. At one year, there were no late complications associated with BASILICA[24]. Specifically, after 30 days there was no stroke, myocardial infarction, coronary intervention, transcatheter aortic valve failure or increase in valve gradients. The coronaries remained clinically patent and there were no BASILICA related deaths.

The international multicenter BASILICA Registry reported results on 214 patients undergoing BASILICA and TAVR in patients at high risk of coronary artery obstruction[4]. 22% were *doppio* (double-leaflet) BASILICA. Procedural success, a composite of successful traversal and laceration, survival and freedom from coronary obstruction or re-intervention was seen in 87%. The 30-day mortality was 2.8% and stroke rate 2.8% (0.5% disabling stroke).

The EURO-BASILICA multicenter registry reported 76 patients at 10 centers undergoing BASILICA and TAVR in patients at high risk of coronary artery obstruction, using commercial off-the-shelf devices [25]. Nine (12%) were *doppio* (double-leaflet) BASILICA. Technical success was 98%, freedom from coronary obstruction was 91%, stroke was 3%. Ten patients required coronary intervention, typically because of avulsed or prolapsed leaflets amenable to orthotopic stenting.

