If there is insufficient charge concentration on the leaflet during laceration, for example when dextrose flush is not used or inner surface denudation is not effectively performed, then the leaflet may avulse through excessive mechanical force. This can cause serious hemodynamic compromise and risk leaflet prolapse into the coronary arteries. This can be avoided with effective insulation and avoiding excessive mechanical force.

We expect this complication to be mitigated by using a purpose-built device.

Mitral apparatus damage

If the guidewire is snared below the level of the LVOT, there is risk of mitral chord entanglement and subsequent laceration leading to severe mitral regurgitation. This complication can be avoided by only snaring the guidewire in the LVOT.

Conventional Treatment Options and Alternatives

Current options for prevention of TAVR-related coronary obstruction include conservative management (essentially palliative care in patients with symptomatic severe aortic stenosis or bioprosthetic valve failure), surgical aortic valve replacement, snorkel stenting, or BASILICA using off-the-shelf equipment off-label.

While surgical aortic valve replacement is an excellent option for some patients, many are at high risk of mortality or morbidity from surgery, often including patients undergoing redo procedures for failing bioprosthetic valves. Many patients demur when offered surgery and insist on a transcatheter alternative.

Snorkel stenting is not a preventative measure but is a bail-out procedure with risks of stent compression, stent under-expansion, thrombosis, loss of coronary access and long term dual antiplatelet therapy.

BASILICA directly addresses the pathophysiology of coronary obstruction but there are no dedicated devices at present to democratize this procedure.

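### The primary efficacy endpoint requires electrosurgical laceration, but its written definition does not test mechanism, so a mechanical tear or avulsion could be scored as device success

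*Combined protocol and SAP*

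**What the plan says.** Section 4.4 builds device technical success from three components: traversal, laceration and retrieval. The bullets for traversal and laceration both carry the word electrosurgical. The supporting definition reads: "Successful laceration is defined as intact liberation of the TELLTALE guidewire loop across a leaflet, with restoration of guidewire mobility", so that the wire can be removed. Transesophageal echocardiography is optional confirmation, and no finding is named that would separate a cut from a tear. The rationale says that the endpoint tests the guidewire alone, against an indication for electrosurgical traversal and laceration.

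Section 4.3 lists three outcomes once the leaflet has been traversed. The second is "Unsuccessful electrosurgical laceration but successful mechanical laceration or avulsion", and its description ends by saying that "mechanical avulsion can be classified as BASILICA technical success according to our definition". Earlier, the same section introduces a list with "Some causes of BASILICA procedure failure despite BASILICA technical success include". The third item there is leaflet protrusion into the coronary artery, either from bulky calcification "or because of mechanical avulsion rather than electrosurgical BASILICA laceration". Section 4.3 also says of the endpoint: "The primary endpoint is selected based on the clinical characteristics and implications of BASILICA success and failure".

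Section 3.2 explains how avulsion arises: if charge concentration on the leaflet is insufficient, "then the leaflet may avulse through excessive mechanical force".

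Under section 11.6 the clinical events adjudication committee (CEAC) reviews the primary efficacy endpoint, and its classification overrides the investigator's. Its charter was to be agreed later and is not in the documents.

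**The concern.** The component and its definition can give different answers for the same patient. An adjudicator who applies the bullet fails an avulsion. One who applies the only written definition of laceration passes it, because the loop came free intact and the wire moved again. The sign of completion in section 7.2, free withdrawal of the guidewire, does not identify mechanism either.

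Section 3.2 attributes avulsion to insufficient charge concentration, which is the function the purpose-built wire is meant to improve. Under the mechanism-blind reading, a failure of that function would be counted as efficacy. The trial is an estimation study (section 10.1), so the proportion with its confidence interval is the primary result, and section 5.3 says that the study is intended to support commercialization.

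**Working it through.** **1. The passages side by side**

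| Place | Treatment of a mechanical laceration or avulsion |
|---|---|
| 4.4, component bullet | Not met: laceration must be electrosurgical |
| 4.4, definition of laceration | Can be met: intact loop release and restored mobility |
| 4.3, outcome (2), label | Electrosurgical laceration unsuccessful |
| 4.3, outcome (2), last sentence | May be classed as BASILICA technical success |
| 4.3, causes of procedure failure | Avulsion can occur despite BASILICA technical success |

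Two rows point to failure and three to success or possible success. The last two rows use a 4.3 term that requires traversal and laceration only; 4.4 adds retrieval and the electrosurgical requirement. No sentence equates the two terms, and none separates them.

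**2. Size of the effect**

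The plan states no figure that depends on this point, so there is none to reproduce. Inputs: N = 90 attempted procedures (section 10.2); a sample proportion with a 95% interval (section 10.4, interval method not named, exact Clopper-Pearson used here); k avulsions counted as failures. The documents give no k for this device, so k is assumed, with no other failures.

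One case: 1/90 = 1.1 percentage points.

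| k | Successes | Rate | Exact 95% CI |
|---|---|---|---|
| 0 | 90/90 | 100% | 96.0 to 100 |
| 1 | 89/90 | 98.9% | 94.0 to 100.0 |
| 3 | 87/90 | 96.7% | 90.6 to 99.3 |
| 5 | 85/90 | 94.4% | 87.5 to 98.2 |
| 9 | 81/90 | 90.0% | 81.9 to 95.3 |

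Under the mechanism-blind definition every row would be reported as 90/90.

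The nearest figure in section 3.2 comes from a 76-patient European registry of off-the-shelf devices: "Ten patients required coronary intervention, typically because of avulsed or prolapsed leaflets amenable to orthotopic stenting". That is 10/76 = 13.2%. It counts coronary interventions, includes prolapse and includes double-leaflet cases, so it is not an avulsion rate. As a loose outer illustration, 0.132 × 90 = 11.8, rounded to 12, gives 78/90 = 86.7% (77.9 to 92.9).

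**3. The exploratory comparison in section 10.4**

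This is a Fisher exact test against the earlier BASILICA IDE study. The comparator is taken as 28/30, the traversal and laceration success in section 3.2. The documents do not say how avulsions were scored there.

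- Comparator left at 28/30, k from 0 to 12: the smallest two-sided p is 0.061, at k = 0; at k = 1 it is 0.154.
- Comparator assumed to lose one success to the same rule (27/30): p = 0.0145 against 90/90 and 0.048 against 89/90.

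The result therefore depends on whether both studies use the same definition.

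**The case against.** The strongest reply is that the better reading already excludes avulsion. The bullet says electrosurgical, section 4.3 calls avulsion an unsuccessful electrosurgical laceration, and the definition can be read as describing when laceration is complete without cancelling the adjective. The traversal definition omits mechanism in the same way. The sentence about technical success concerns a differently named construct. All of this stands, and it is why the point is a conflict in wording. A reader might infer that the protocol instructs avulsions to be counted as primary successes; the documents do not say that. What remains is that the definition, applied as written, allows it.

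A second reply is that avulsion is captured elsewhere. Section 3.3 lists leaflet avulsion among the anticipated adverse device effects, and section 9.4 requires such effects to be recorded. Section 4.3 classes procedures with orthotopic stenting as unsuccessful. The primary safety endpoint counts coronary obstruction and related reintervention, and the exploratory endpoints include stenting and hemodynamic deterioration before TAVR. These sources would show many of the cases. They do not settle the primary efficacy score: 4.3 says stenting is needed only sometimes, and the stenting rule is not carried into 4.4.

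A third reply is that the CEAC charter may contain a mechanism rule. It may. That charter cannot be checked here, and the endpoint definition should not depend on it.

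A fourth reply is that mechanism can be hard to judge, because laceration combines electrosurgery with traction and the core-laboratory fluoroscopy reads named in section 9.2 are coronary patency and ostial engagement. This also stands. Scoring every undetermined case as a failure would stretch the missing-data rule of section 10.4 and bias the rate downward, so such cases are better shown both ways.

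**Conclusion.** The point holds as an unresolved conflict between the 4.4 component and its definition, made worse by the 4.3 sentence on technical success. The weight of the text favors failure, but the written definition allows success, and that scoring would overstate device performance for an electrosurgical indication. It should be fixed. The size is 1.1 points per case at N = 90; the total depends on an avulsion count that the documents do not give.

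Three stronger readings are not supported.

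- **That the interim result is inflated.** Section 3.2 reports 100% primary success in 27 treated subjects from non-adjudicated data and mentions no avulsion. Whether any occurred is unknown.
- **That a trial conclusion would flip.** There is no performance goal and no powered test, so only the estimate, its interval and one exploratory comparison are affected.
- **That the Fisher comparison is safely non-significant whatever is done.** That holds only with the comparator left at 28/30 and no other TELLTALE failures over the assumed range. One reclassified comparator success changes it.

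**What to change.** 1. Add to the laceration definition in 4.4 that mechanical laceration or avulsion does not meet the electrosurgical laceration component. State in 4.3 that BASILICA technical success is not the 4.4 endpoint.
2. Have the CEAC apply this rule, using the procedure fluoroscopy, the hemodynamics recorded between laceration and TAVR (section 7.2), and the adverse-device-effect reports of avulsion.
3. Report the numbers of mechanical and undetermined cases. Give the success rate with undetermined cases counted as successes and as failures. Add one sensitivity analysis, with exact interval, under the mechanism-blind definition.
4. In the exploratory Fisher comparison, use the same laceration definition in both studies, or state that the comparator's scoring of avulsions is unknown.
5. Disclose that the clarification was made in an open-label study after interim outcomes were seen. Relative to the mechanism-blind reading, the rule in item 1 can only lower the TELLTALE rate or leave it unchanged.

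Cost: a sentence each in 4.3 and 4.4, the same rule for the CEAC, and an amendment with IRB approval. The inputs are records the protocol already calls for. The headline rate may be slightly lower, and some cases may remain undetermined because echocardiography during the procedure is used as needed and there is no echocardiography core laboratory.
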